15.4.3 Secondary Endpoints (Immunological Endpoints)

The secondary objectives are:

- To evaluate the IgG antibody response to the GBS-NN/NN2 vaccine at Day 85 (most important immunological endpoint).
- To assess whether pre-existing antibody levels affect the vaccine-induced antibody response.

Immunological parameters measured to evaluate objectives

In order to evaluate these objectives, GBS-NN and GBS-NN2 specific IgG concentrations will be determined by ELISA against a reference standard human antibody preparation of known concentration as described in the laboratory protocol and used to derive the following parameters for each subject:

- Antibody concentrations specific for GBS-NN and GBS-NN2 at each sample point ($\mu\text{g/mL}$)
- Fold increases over pre-immunisation level (Day 1) in antibody concentrations at each sample point (ratio)

Specific Endpoints calculated from immunological parameters

These parameters will be used to derive the following endpoints at all time-points according to the treatment group:

- Geometric mean antibody concentrations specific for GBS-NN and GBS-NN2 in $\mu\text{g/mL}$ (with 95% CI).
- Geometric mean fold increase in antibody concentration (with 95% CI).
 - Seroconversion rate (proportion of subjects with fold increase above threshold at any time point post vaccination up to Day 85).
- Proportion of subjects achieving antibody concentrations above specific thresholds at Days 29 & 85 (these will be 2, 4, 8 $\mu\text{g/mL}$). This will provide an assessment of the immune response to the first and second doses.

The most important immunological end point will be the values of these end points at Day85, 12weeks after the administration of the first dose of vaccine.

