24 HOUR SPONSOR MEDICAL MONITOR

[REDACTED]

SAFETY REPORTING

[REDACTED]

SAFETY LABORATORIES

[REDACTED]

STATISTICS

[REDACTED]

ANALYSIS OF PHARMACODYNAMIC BLOOD SAMPLES

[REDACTED]

And

[REDACTED]

[REDACTED]

	
 • Geometric mean fold increase in antibody concentration. • Seroconversion rate (proportion of subjects with fold increase above threshold at any time post vaccination). • Proportion of subjects achieving antibody concentrations above specific thresholds at Days 29 & 85 (these will be 2, 4, 8 µg/mL). This will provide an assessment of the immune response to the first and second doses. 									
Study Design:	
This is a Phase I, randomised, double-blind, placebo-controlled, parallel group, single centre study.
 
There will be 2 cohorts of 30 subjects. Cohort 1 will receive two 0.5 mL injections, 4 weeks apart, each consisting of 25 µg of GBS-NN and 25 µg of GBS-NN2 (24 subjects) or placebo (6 subjects). Cohort 2 (30 subjects) will receive two 0.5 mL injections, 4 weeks apart, each consisting of 50 µg of GBS-NN and 50 µg of GBS-NN2 (24 subjects) or placebo (6 Subjects). All vaccines will be adsorbed to 500 µg Al3+ as Alhydrogel®.
 
Safety will be assessed after all subjects have completed Visit 4 (Day 8) for Cohort 1, at which point the decision will be made as to whether proceeding with administration of the doses in cohort 2 is appropriate.
									
Study Duration:	Study start is defined as check-in to the study unit on Day 1. Each individual subject will be involved in the study for approximately 12 weeks (excluding the 28 day screening period and the 6 month safety follow up).									
Study Population:	60 healthy female subjects aged 18 to 40 will be randomised into 2 cohorts of 30 subjects.									
Investigational Medicinal Product and mode of administration	
GBS-NN/NN2 vaccine will be supplied [REDACTED]
 
The placebo vaccine will contain Alhydrogel® mixed with sterile dilution buffer.
									

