
Statistical Analysis:
	
Statistical analyses will be performed by [REDACTED] using SAS 9.3 or higher. Descriptive statistics for quantitative parameters will be provided using number of observations (N), mean, standard deviation (SD), minimum, median and maximum. Descriptive statistics for qualitative parameters will be provided using absolute frequencies (n) and relative frequencies (%). For immunological endpoints (IgG concentration and fold increase) additionally geometric means with corresponding 95% confidence intervals will be presented.
 
Demographic, baseline characteristics and data recorded during the study will be summarized using descriptive statistics by treatment (placebo or vaccine) and dose group, unless otherwise specified. Individual data will be presented as a data listing, sorted by treatment and administered dose level.
 
For parameters with evaluation before vaccination and in case of re-checked value(s), only the last observation prior to dosing will be used in descriptive and inferential statistics and derivations of other parameter values. After vaccination, only values of scheduled assessments (planned in the protocol) will be used.
 
Statistical tests will be carried out to compare results between treatment groups, depending on studied variable type. These analyses will be fully detailed in the SAP.
 
For categorical endpoints, such as local and systemic reactogenicity, a comparison of events intensity (scores) between vaccine dose groups can be performed with an adequate statistical test dealing with categorical variables (for example: Fisher exact test, Chi square test or generalized estimating equations).
 
For continuous endpoints, such as immune response induced by different GBS-NN/NN2 vaccine dosing regimens, appropriate statistical method (for example: ANOVA or ANCOVA) can be used to compare pre-vaccination and post-vaccination levels as well as post-vaccination levels between groups.

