7.2 Secondary Objectives

- To evaluate IgG antibody responses induced by the two vaccine doses of GBS-NN/NN2 up to Day 85 in healthy female subjects.
- To assess whether pre-existing antibody levels affect the vaccine-induced antibody response.

7.3

pregnancy.

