12.2 Treatment Period and Post-Study Period

Subjects will be administered the primary dose of the appropriate dose of GBS-NN/NN2 or placebo according to the cohort and dosing schedule described in section 10.1 at Visit 2 and a second dose will be administered at Visit 6. All cohorts will incorporate sentinel dosing of 2 subjects in each cohort for the primary dose only: 1 on active treatment and 1 on placebo. No further subjects in that cohort will be dosed until 24 hours after dosing the second subject, provided that there are no serious or unexplained safety issues as determined by the Investigator.

The decision to proceed with administration of the primary dose in the subsequent cohort will be made as described in Section 12.5.

The following assessments will be carried out at these visits:

Visit 2

A general medical review, vital signs, urine pregnancy test, urine drugs of abuse test and alcohol urine test will be performed to re-confirm eligibility. Eligible subjects will then be randomised to receive the appropriate treatment as per the randomisation list for the cohort. A pharmacodynamic blood sample will be taken to measure pre-existing antibody levels and to obtain Peripheral Blood Mononuclear Cells (PBMCs) to assess cellular responses, prior to

dosing. Blood sample for haematology and serum biochemistry will be taken. Vital signs will be recorded at pre-dose (within 60 minutes of dosing), 2 (± 0.25) and 4 (± 0.25) hours post-dose. A general medical examination (including an assessment of the injection site) will be performed prior to discharge to ensure the subject is fit for discharge. At discharge subjects will be provided with oral temperature kit and instructed to record a temperature if they feel unwell in the seven days post dose.

Visit 3

Visit 3 will be performed 24 hours (± 2 hours) after administration of the primary dose and an assessment of the injection site will be performed, vital signs will be recorded and AEs and concomitant medications will be reviewed.

Visit 4

Visit 4 will be performed 1 week (± 1 day) after administration of the primary dose. An assessment of the injection site will be performed, vital signs will be recorded, safety blood samples for haematology and biochemistry will be collected, urinalysis will be performed and AEs and concomitant medications will be reviewed.

Visit 5

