15. STATISTICAL EVALUATION

Details of the planned statistical analyses will be described in the Statistical Analysis Plan (SAP) and some important features are presented in this protocol. Statistical analyses will be performed by ████████ using SAS version 9.3.

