15.1.3 Inferential statistics

Statistical tests will be carried out to compare results between treatment groups, depending on studied variable type. These analyses will be fully detailed in the SAP.

For categorical endpoints, such as local and systemic reactogenicity, a comparison of events intensity (scores) between groups can be performed with an adequate statistical test dealing with categorical variables (for example: Fisher exact test, Chi square test or generalized estimating equations).

For continuous endpoints, such as immune response induced by different GBS-NN/NN2 vaccine dosing regimens, appropriate statistical methods (for example: ANOVA or ANCOVA) can be used to compare pre-vaccination and post-vaccination levels as well as post-vaccination levels between groups.

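### Sequential dose cohorts are described as randomised, and the visible plan names no analysis of response against Day 1 IgG and leaves baseline adjustment of IgG comparisons optional

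*Combined protocol and SAP*

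**What the plan says.** **Second secondary objective.** Section 7.2 sets it as "To assess whether pre-existing antibody levels affect the vaccine-induced antibody response", and Section 15.4.3 repeats it. Section 15.4.3 derives two parameters for each subject: IgG concentration, and fold increase over her own Day 1 level. It continues: "These parameters will be used to derive the following endpoints at all time-points according to the treatment group". The endpoints are geometric mean concentration, geometric mean fold increase, seroconversion rate and the proportions above 2, 4 and 8 µg/mL. Day 85 is named as the most important time point.

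**Method for IgG comparisons.** Section 15.1.3 gives examples only: "for example: ANOVA or ANCOVA) can be used to compare pre-vaccination and post-vaccination levels as well as post-vaccination levels between groups". The Synopsis says the same. Neither names a covariate or a scale. Section 12.2 provides the baseline at Visit 2, before dosing: "A pharmacodynamic blood sample will be taken to measure pre-existing antibody levels".

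**Deferral.** Section 15 opens with "Details of the planned statistical analyses will be described in the Statistical Analysis Plan (SAP) and some important features are presented in this protocol". No separate SAP was available. Sections 7.3 to 8.2 are missing from the public text and the exploratory endpoints in Section 15.4.4 are redacted. None of this is a fault in the plan, but it limits what can be concluded.

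**Randomisation.** The Synopsis and Section 9.3 state "60 healthy female subjects aged 18 to 40 will be randomised into 2 cohorts of 30 subjects", and Section 15.2 defines the Randomized Set (RAN) by randomisation at Visit 2 to one of the two cohorts. Section 12.2 describes something different: "Eligible subjects will then be randomised to receive the appropriate treatment as per the randomisation list for the cohort". The Synopsis and Section 12.5 make cohort 2 conditional on a safety review of cohort 1 through Day 8.

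**The concern.** A group summary of fold increase divides by baseline but does not show whether women with high Day 1 IgG respond differently from women with low Day 1 IgG. If nothing more is specified, a formal secondary objective ends without a result. The obvious improvised analysis, relating fold rise to Day 1, is also the misleading one.

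Leaving plain ANOVA open gives up precision that an already scheduled sample could supply, and it leaves the model to be chosen later for the endpoint the plan ranks highest among the immunological ones.

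The randomisation wording matters because Section 15.1.3 contemplates comparing dosing regimens. Described as randomised, a 25 versus 50 µg difference would be read as a dose effect. With sequential cohorts it could also reflect when the women were enrolled.

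**Working it through.** **1. Design figures.** Each cohort has 24 vaccinees and 6 placebo subjects, so 2 × (24 + 6) = 60, as stated. The visible text gives no SD, correlation, power or effect size, so there is no power-based figure to reproduce. SDs and correlations below are assumptions, shown as ranges.

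**2. Randomisation passages side by side.** A woman attending Visit 2 while cohort 1 is enrolling cannot be allocated to cohort 2, which has not been approved to start. She is allocated from her cohort's list, to vaccine or placebo. So the Synopsis (study population), 9.3 and 15.2 cannot be read literally together with the Synopsis (study design), 12.2 and 12.5. Every subject is still randomised, so RAN contains the same women either way.

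**3. Would each cohort's own placebo group rescue the dose comparison?** For the direct contrast the variance factor is 2/24 = 0.083. Anchored on placebo it is 2/24 + 2/6 = 0.417, so the SE rises by √(0.417/0.083) = 2.24. The smallest ratio detectable at 80% power, two-sided 5%, is 10^((1.96 + 0.84) × SD × √factor). At an assumed log10 SD of 0.4 it goes from 2.1 to 5.3. Six placebo subjects per cohort cannot carry that load.

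**4. Why fold rise should not be related to Day 1.** Let k = SD(post)/SD(pre) on the log scale and ρ = the correlation of pre with post. Then corr(log fold, log Day 1) = (ρk − 1)/√(k² + 1 − 2ρk). With ρ = 0:

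- k = 0.5: −1/√1.25 = −0.89
- k = 1: −1/√2 = −0.71
- k = 2: −1/√5 = −0.45

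A strong negative correlation appears even though the Day 85 level is unrelated to Day 1.

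**5. What the regression would deliver.** Regress log10 Day 85 on log10 Day 1 with dose group, in 48 vaccinees. A slope of 0 means the Day 85 level does not depend on Day 1; a slope of 1 means the fold rise does not. By simulation at ρ = 0.3, the mean 95% CI half-width is 0.29, 0.43 and 0.57 for k = 1, 1.5 and 2. At k = 2, 19% of intervals cover both 0 and 1. Assay error shrinks the slope in proportion to the reliability of Day 1 IgG: a true slope of 1 averages 0.90 at reliability 0.9 and 0.80 at 0.8.

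**6. ANCOVA against ANOVA, 24 versus 24, no Day 1 shift.** Expected variance ratio = (1 − ρ²)(1 + 1/44), where the second factor is the price of estimating the slope.

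- ρ = 0: 1.02
- ρ = 0.3: 0.91 × 1.023 = 0.93
- ρ = 0.5: 0.75 × 1.023 = 0.77
- ρ = 0.7: 0.51 × 1.023 = 0.52

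Simulation agrees to within about 0.01. The 95% CI factor on the geometric mean ratio is 10^(t × SD × √(2/24 × ratio)). At an assumed log10 SD of 0.5, ANOVA gives ×/÷ 1.95 (t = 2.013, 46 df). ANCOVA (t = 2.014, 45 df) gives 1.91, 1.80 and 1.62 for ρ = 0.3, 0.5 and 0.7.

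**7. What ANCOVA does not do.** Suppose there is no dose effect and no Day 1 shift, but enrolment period moves Day 85 IgG directly by 0.25 SD (assumed). ANOVA noncentrality is 0.25/√(2/24) = 0.87, which rejects in about 14% of trials. Simulated ANCOVA rejects in about 14%, 16% and 21% at ρ = 0.3, 0.5 and 0.7, because it measures the same bias more precisely.

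**The case against.** The strongest reply is that the protocol claims to give only some features and sends the rest to an SAP. Silence with explicit deferral is not an error, and protocol sections are missing from the public text as well. This stands for the two analysis points, which are conditional on what the SAP contains. It does not touch the randomisation wording, which is a contradiction within the protocol.

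A reader might infer that the plan ignores the link between response and baseline altogether. It does not: a fold increase over her own Day 1 level is derived for each subject, and ANCOVA is named as an option. What is absent is a named analysis of response as a function of Day 1.

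A reader might also infer that ANCOVA would hold the false-positive rate of the dose comparison near 5%. That is true only if cohorts differ solely through Day 1 IgG, which the documents do not establish; step 7 shows the opposite case.

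It can fairly be said that the precision gain is small at ρ = 0.3 (×/÷ 1.95 to 1.91), that the documents support no particular correlation, and that a single centre with one set of eligibility criteria may show little drift between cohorts. All of that stands. It is also fair that the escalation design is described plainly elsewhere, and that correcting the wording changes no analysis set.

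**Conclusion.** The point holds within limits.

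- **Randomisation wording:** established from the protocol alone. RAN membership does not change; what the 25 versus 50 µg comparison can claim does. A reader might go further and infer that the trial is not randomised, or that the plan expressly calls the dose contrast a randomised one. Neither is supported: vaccine versus placebo is randomised within each cohort, and the fault lies in the phrases that place randomisation at cohort level.
- **Second secondary objective:** the listed endpoints give no result for it, unless the SAP or the missing sections add an analysis.
- **Baseline adjustment:** near-free and worth fixing in advance. The variance is about 0.93 to 0.52 of ANOVA for an assumed correlation of 0.3 to 0.7, against a penalty of about 2% at zero correlation. The case is one of precision, not protection against cohort effects.

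All three bear on secondary immunogenicity results. The primary safety objective is unaffected. The change should be made; confidence is medium because the SAP was not available.

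**What to change.** 1. In Section 15.2, define RAN as subjects randomised to vaccine or placebo within a cohort. Correct the Synopsis and Section 9.3 to match, and report 25 versus 50 µg as a non-randomised comparison.
2. In Section 15.4.3, for the second objective and each antigen, report in vaccinees the slope of log10 Day 85 IgG on log10 Day 1 IgG, adjusted for dose group, with 95% CI. Treat it as estimation, given the widths in step 5. Do not relate fold rise to Day 1. State how many Day 1 values lie below the LLOQ (Section 15.2 allows these to be replaced) and that assay error pulls the slope toward 0. Further sensitivity analyses are optional.
3. In Sections 15.1.3 and 15.4.3, make between-group comparisons of Day 85 IgG an ANCOVA on log10 concentration with log10 Day 1 concentration as covariate. Report adjusted geometric mean ratios with 95% CI, and say that the adjustment covers measured Day 1 differences only.

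The cost is wording, one regression and one ANCOVA per antigen, and a count of Day 1 values below the LLOQ. No new samples are needed. If the SAP already specifies items 2 and 3, only item 1 remains.

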15.4.4 Exploratory endpoints

Exploratory Objectives

- | [REDACTED]

Endpoints to be measured to assess the exploratory endpoints:

- [REDACTED]
- | [REDACTED]
- | [REDACTED]

16. ETHICS AND REGULATORY

16.1 Conduct

This study will be conducted in accordance with the standard operating practices of the Sponsor and Contract Research Organisation(CRO), which are designed to ensure adherence to Good Clinical Practice (GCP) guidelines as required by the following:

1. Declaration of Helsinki, 1964 (“Recommendations Guiding Physicians in Biomedical Research Involving Human Patients”), and all its accepted amendments to date concerning medical research in humans.
2. ICH E6 Guideline for GCP and subsequent notes for guidance (CPMP/ICH/135/95) European Agency for the Evaluation of Medicinal Products, Committee for Proprietary Medicinal Products, International Conference on Harmonisation of Pharmaceuticals for Human Use. (Note for Guidance on Good Clinical Practice, 2002).
3. European Union (EU) Clinical Trials Directive 2001/20/EC on the regulation of clinical trials in the EU and the implementation of GCP.
4. GCP Directive 2005/28/EC.

This study will be conducted in accordance with national and local laws (e.g. drug and narcotics laws) of the countries where study sites are located.

The Investigator agrees, when signing the protocol, to adhere to the instructions and procedures described in the protocol and to adhere to the principles of ICH Good Clinical Practice to which the protocol conforms as well as all governing local regulations and principles for medical research.

16.2 Review

The protocol, any protocol amendments, subject information sheet (VIS), informed consent form (ICF) and any study related information or documents issued to subjects will be reviewed and approved along with other required documents by the Ethics Committee (EC) and each study site’s local EC before subjects are screened for entry. The ECs should be constituted and functioning in accordance with ICH E6, Section 3.2, and any local regulations. The EC that provides a positive opinion for this study will be included in the clinical study report for this protocol.

A signed letter of positive opinion regarding the study from the EC Chairman must be sent to the Investigator who will provide the Sponsor with a copy. The Investigators or Sponsor will submit, depending on local regulations, periodic reports and inform the EC of any reportable AEs per ICH guidelines and local EC standards of practice.

SAEs should be reported to the EC in accordance with local regulatory requirements.

In the case of early termination/temporary halt of the study, the Investigator should notify the EC and the Sponsor should notify the Competent Authority (CA) within 15 days and a detailed written explanation of the reasons for the termination/halt should be given. If the EC decides to suspend or terminate the study, the Investigator will immediately send the notice of study suspension or termination by the EC to the Sponsor.

At the end of the study, the EC and CA will be notified within 90 days. The end of the study will be the date of the last study visit for the last subject in the study. The Sponsor will always also provide the EC/CA with a summary of the study’s outcome.

16.3 Subject Information and Informed Consent

Informed consent should be obtained by means of a VIS and ICF, prepared in accordance with ICH E6 (R2) Section 4.8.10 and applicable local regulations, written in non-technical language. All subjects will be provided with oral and written information describing the nature and duration of the study and the procedures to be performed. The subject will be asked to sign and date an ICF prior to any study-specific procedures being performed. No subject can enter the study before his/her informed consent has been obtained. A sample subject ICF used in the study will be included in the clinical study report for this protocol.

Prior to study start, the subjects will receive a full explanation of the nature of the study, its purpose, the procedures involved, the expected duration, the potential risks and benefits involved, and any potential discomfort. Each subject must be informed that participation in the study is voluntary and that he/she may withdraw from the study at any time and that withdrawal of consent will not affect his/her subsequent medical treatment or relationship with the treating physician. The subject should understand the VIS and ICF before signing and dating the ICF. The Investigator or qualified person obtaining consent must also sign and date the form. Each subject will be given a copy of the signed informed consent and written information.

The original signed ICF for each subject will be verified by the Sponsor monitors and kept in the study centre investigational site files.

